4 STUDY DESIGN**4.1 OVERALL DESIGN**

We will conduct a dialysis clinic-level cluster randomized trial with two groups, SPIRIT versus usual care followed by delayed SPIRIT. We will recruit 400 dyads of patients on chronic (“prevalent”) dialysis who are at high risk of death in the next year and their surrogate decision-makers (total 800 individuals) from 30 free-standing dialysis clinics in 4 states. The primary outcomes are patient and surrogate self-report preparedness for end-of-life decision making. The implementation evaluation data will be obtained throughout the study course. Upon patient death (anticipate 20% of patients; n = ~ 80), we will assess surrogates’ post-bereavement distress. Patient participation will end at 9 months (to allow for obtaining Medicare claims data during the study period) or death, whichever occurs first; surrogate participation will end at 9 months or at the completion of 3-month post-death follow-up. If patient is still living at 9 months, we will ask for an extension of follow up period to include 12 more months. Medicare claims data for end-of-life treatment intensity will be obtained quarterly. Clinics assigned to usual care will receive the delayed implementation, SPIRIT, in Year 4, Q1. This is a Phase III trial of an intervention that involves minimal risks and has proven to be efficacious, and thus no interim analysis is planned.

For Supplement Aims:

We will use a randomized controlled trial design with two groups: SPIRIT-dementia and usual care. From the pool of screened but excluded ESRD patients, we will recruit 30 dyads of patients with mild to moderate dementia and their surrogates. The groups will be stratified by race (white vs non-white). Patient and surrogate self-reported preparedness for end-of-life decision making will be measured at baseline and shortly after the intervention (by phone in the next 2-3 days) as done in the pilot test of SPIRIT-dementia. Additionally, we will review the patient's medical record to examine care decisions at 6 months or after the patient's death, whichever occurs first. In the case of patient death, we will also assess surrogates' post-bereavement outcomes (anxiety and depression symptoms) at 1 month after the patient's death. Based on previous research,¹³ we anticipate about 50% of the supplement sample will die within 12 months of enrollment. All data collection from study participants will be telephone-based.

Supplement cohort study:

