8 STUDY ASSESSMENTS AND PROCEDURES

8.1 OUTCOME ASSESSMENTS

Collecting effectiveness outcome data will be centralized; research staff at the Study Coordinating Center will collect the data from patients and surrogates by phone. Telephone-based collection minimizes participants' travel burden. Centralized data collection maintains data collectors being blind to group assignment. The preparedness outcomes will be assessed at 2 weeks post-intervention, as in our R21 trial.¹⁸ We expect roughly 40% of study patients (~160) to die by the 9-month follow-up; deaths are readily identifiable through dialysis clinics and will trigger post-bereavement surveys with surrogates at 3 months and staggered CMS data collection. Post-bereavement assessment at 3 months is based on our efficacy data showing that distress symptoms sharply rose in both groups 2-weeks post-bereavement and then stabilized at 3 months.

Effectiveness Outcomes

Preparedness for end-of-life decision making (measured at baseline and 2 wks post-Session II):

- **Dyad congruence** will be assessed using the Goals-of-Care Tool,^{18,20} which includes two scenarios describing medical conditions commonly occurring in ESRD patients. In the first, the patient develops a severe complication and cannot speak for himself/herself; the medical team believed recovery unlikely and continuing life-sustaining treatment, including dialysis, would no longer be beneficial. In the second scenario, the patient develops advanced dementia. Each scenario has three response options: "The goals of care should focus on delaying my death, and thus I want to continue life-sustaining treatment", "The goals of care should focus on my comfort and peace, and thus I do not want life-sustaining treatment, including dialysis", and "I am not sure". Patients and surrogates complete this tool independently and their responses are then compared to determine dyad congruence -- either congruent in both scenarios or incongruent. If both members of the dyad endorse "I am not sure", they are considered incongruent.
- **Patient decisional conflict** will be measured using the 13-item Decisional Conflict Scale (DCS), a validated measure in the context of end-of-life decision making¹⁷; higher scores indicate greater difficulty in weighing benefits and burdens of life-sustaining treatments and decision making (range 1-5; Cronbach's $\alpha = 0.8 - .93^{17,18,20,72}$).

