9.2 SAMPLE SIZE DETERMINATION

We have an adequate sample size to detect clinically meaningful differences between SPIRIT and usual care for our primary outcomes. Statistical power is based on a random effects models: a generalized linear mixed model for binary outcomes (e.g., dyad congruence) and a linear mixed model for continuous outcomes (e.g., patient decisional conflict).

We conducted a simulation study to estimate power with 2-sided significance level alpha=.05, corrected for anticipated dropout and potential intraclass correlations (ICCs) ranging .01-.04, based on ICCs observed in our prior work. To estimate the power more conservatively, we used the effect sizes observed at 2 months²⁰ rather than those at 2 weeks,¹⁸ which are larger (e.g., for the composite outcome, *OR*=1.8 at 2 months, *OR*=4.4 at 2 weeks). The overall power to detect clinically meaningful differences is excellent for the primary outcomes and good for the post-death outcomes.

Power for comparing SPIRIT and usual care with 19 clusters				
Aim 1	Percent or min. difference	OR or variance	ICC ^a	Estimated power
Dyad congruence	48%	OR =2.0	0.02 0.04	0.92 0.84
Patient DCS	d =0.24	0.23	0.01 0.10	0.98 0.81
Surrogate DMC	d =0.22	0.20	0.01 0.10	0.99 0.80
Composite outcome	47%	OR =2.0	0.02	0.93
Aim 3				
Anxiety	d =1.35	7.0	0.01 0.03	0.84 0.80
Depression	d =1.60	10.0	0.01 0.03	0.85 0.79
PTSS-10	d =4.75	90.0	0.01 0.03	0.85 0.78

^a observed ICCs in our prior work; *d*=1/2 *SD*.

DCS, decisional conflict scale; DMC, decision-making confidence.

For Supplement Aims:

Because this is a pilot study, prior estimates of effect sizes were not available; thus a traditional sample size calculation was not performed. Instead we focused on calculating the minimum effect size that can be detected with adequate power (>=80%). Based on preliminary calculations, we found that a sample size of 30 will achieve 80% power to detect an effect size (Cohen's *f*²) of 0.28 (moderate-high), attributable to the treatment group indicator using an F-test at a 5% significance level. We will use the estimates of effect sizes obtained from this study for sample size calculations in future larger studies.

Supplement cohort study:

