9.4.3 ANALYSIS OF THE SECONDARY ENDPOINT(S)

Analysis of secondary endpoints are not dependent on findings of primary endpoints.

SPIRIT effectiveness on surrogates’ post-bereavement psychological distress: We will use the same approach as in the analysis of the primary endpoints to compare anxiety, depression, and post-traumatic distress symptoms in SPIRIT vs usual care among surrogates of patients who die during the initial implementation and 9-month (or extended) follow-up.

Implementation process outcomes: Quantitative data on acceptability, fidelity, and costs of SPIRIT will be summarized using descriptive statistics. SPIRIT will be determined to be acceptable to care providers and patients and surrogates if over 75% of responses exceed an average summative score ≥ 3 (of 4) on the acceptability measures. Cost estimates will be used to ascertain resources needed to implement or replicate SPIRIT in the

future.⁹² We will also explore the relationships of these quantitative data with characteristics of settings and stakeholders. Transcripts of acceptability interviews will be transferred to ATLAS.ti for analysis. Content analysis techniques⁹³ will be used without preconceived categories.⁹⁴ Open coding will be applied⁹⁵ and disagreements on coding will be resolved by consensus. We will examine the data for patterns or differences in themes between those with acceptability scores ≥ 3 and scores < 3 and setting characteristics. This analysis will be facilitated by creating matrixes that organize textual and numeric data for comparing and contrasting⁹⁶ so that what contributed to acceptability scores that are positive and less than positive may be identified. We will use a similar approach, content analysis, to evaluate the sustainability data.

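### Sections 4.1 and 8.1 expect about 80 and about 160 deaths; section 9.2 names neither, and its Aim 3 power fits only the larger count (at 80, unadjusted, about 0.52 to 0.61)

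*Combined protocol and SAP*

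**What the plan says.** Section 4.1 (Overall Design) gives the expected deaths as "anticipate 20% of patients; n = ~ 80" and sets no time limit on that figure. The same paragraph adds: "If patient is still living at 9 months, we will ask for an extension of follow up period to include 12 more months".

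Section 8.1 (Outcome Assessments) says: "We expect roughly 40% of study patients (~160) to die by the 9-month follow-up". Those deaths trigger the 3-month bereavement survey.

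Section 9.2 (Sample Size Determination) describes the method: "We conducted a simulation study to estimate power with 2-sided significance level alpha=.05, corrected for anticipated dropout". Its table is headed "Power for comparing SPIRIT and usual care with 19 clusters". For Aim 3 it lists a difference, a variance, two ICCs and two powers per outcome, and a footnote equates the difference with half an SD. It gives no number of deaths or bereaved surrogates, yet concludes: "The overall power to detect clinically meaningful differences is excellent for the primary outcomes and good for the post-death outcomes".

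Section 9.4.3 defines the Aim 3 analysis set as "surrogates of patients who die during the initial implementation and 9-month (or extended) follow-up".

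**The concern.** The two expected counts differ by a factor of two and refer to the same 400 patients. Follow-up length does not reconcile them. The larger count is tied to the shorter, explicit window of 9 months. The smaller has no window and stands beside a 12-month extension, which can only add deaths.

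Aim 3 carries three secondary hypotheses: anxiety, depression and post-traumatic distress. Its power depends mainly on the number of bereaved surrogates. If about 160 is meant, the table is roughly right. If about 80 is meant, the trial has little better than an even chance of detecting a half-SD difference, and a null result on bereavement distress would be hard to interpret. The DSMB is asked in section 10.1.6 to compare the sample with the power assumptions, and it cannot do so for Aim 3 while this assumption is unstated.

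**Working it through.** **Inputs.** All are from the section 9.2 table unless noted.

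- Differences and variances: anxiety 1.35 and 7.0; depression 1.60 and 10.0; PTSS-10 4.75 and 90.0.
- ICC 0.01 and 0.03; 19 clusters; two-sided alpha 0.05.
- Bereaved surrogates D: 80 (section 4.1) or 160 (section 8.1).
- Assumed: equal arms, similar cluster sizes, no baseline adjustment, every bereaved surrogate analysed.

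**Standardised differences.** 1.35/√7 = 0.510; 1.60/√10 = 0.506; 4.75/√90 = 0.501. These agree with the half-SD footnote.

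**Formulas.** Design effect DE = 1 + (D/19 − 1) × ICC. Noncentrality = δ × √(D / (4 × DE)). Power comes from the normal distribution, or from the noncentral t with D − 2 degrees of freedom or with 17 (clusters minus 2).

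**Reproducing the plan's figures.** Solving for the D that gives each stated power:

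- normal: 142 to 153 surrogates
- D − 2 df: 145 to 156
- 17 df: 163 to 175

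Together that is about 36% to 44% of 400. As a direct check, at D = 150 (160 less about 6% loss, an assumed rate) the normal approximation gives 0.856/0.812, 0.850/0.805 and 0.843/0.797, all within 2 percentage points of the table.

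**One value in full at D = 80** (anxiety, ICC 0.01). DE = 1 + (80/19 − 1) × 0.01 = 1.032. Noncentrality = 0.510 × √(80 / (4 × 1.032)) = 2.25. Normal power = Φ(2.25 − 1.96) ≈ 0.61. The plan states 0.84.

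**All outcomes at D = 80, power at ICC 0.01 / 0.03**

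| Outcome | Stated | Normal | 78 df | 17 df |
|---|---|---|---|---|
| Anxiety | 0.84 / 0.80 | 0.61 / 0.59 | 0.60 / 0.58 | 0.56 / 0.54 |
| Depression | 0.85 / 0.79 | 0.61 / 0.58 | 0.59 / 0.57 | 0.56 / 0.53 |
| PTSS-10 | 0.85 / 0.78 | 0.60 / 0.57 | 0.59 / 0.56 | 0.55 / 0.52 |

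A simulation at D = 80 (19 clusters of random size, known ICC, 4,000 runs, anxiety and PTSS-10) gave 0.56 to 0.60.

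**At D = 160.** Power is 0.81 to 0.88 (normal or 158 df) and 0.77 to 0.84 (17 df), which brackets the table.

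**Detectable difference at D = 80, 80% power.** 0.64 to 0.66 SD (normal or 78 df); 0.68 to 0.70 SD (17 df).

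**Other readings at D = 80 (normal).** Ignoring clustering gives 0.61 to 0.63. One-sided testing gives 0.69 to 0.73. Neither reaches the stated values.

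**The case against.** The best defence is baseline adjustment. HADS and PTSS-10 are collected at baseline, the prior trial's bereavement results were adjusted for baseline values, and section 9.2 reports a simulation whose details are not given. If the simulation adjusted for baseline, 80 surrogates could reach the stated power, but only with a baseline-to-3-month correlation of about 0.62 to 0.72. The documents state no such value. The only between-measurement correlation used in any of their power calculations is 0.2, for the cohort supplement; at D = 80 it gives 0.59 to 0.63 (normal). The half-SD footnote, which matches the listed variances, also points to an unadjusted calculation. That is an inference, so the conclusion here carries the condition.

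Three smaller points have some force.

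- Seventeen degrees of freedom is conservative when there are about four deaths per cluster and the ICC is small. The simulation suggests 0.56 to 0.60 is more realistic than 0.52.
- The cluster counts by state in section 6.3 sum to 4 + 3 + 8 + 5 + 8 = 28, not 19. With 28 clusters, power at 80 moves only to about 0.56 to 0.62.
- The amendment history shows that the investigators saw too few deaths and extended follow-up for that reason. It gives no replacement count, so the inconsistency remains.

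It is also fair to say that no arithmetic in section 9.2 is shown to be wrong. The fault is an unstated input and two incompatible values for it.

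**Conclusion.** The concern holds. The Aim 3 power of 0.78 to 0.85 is consistent with the roughly 160 deaths of section 8.1 and not with the roughly 80 of section 4.1. At the smaller count the shortfall is about 20 to 30 percentage points, depending on outcome, ICC and method. This rests on the listed variances, equal arms, similar cluster sizes and no baseline adjustment, and it uses closed-form approximations to a simulation that is not described in full. Treating all 80 surrogates as analysed is generous, since any loss before the 3-month survey lowers power further. The matter should be fixed, but it is confined to secondary endpoints.

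**What to change.** 1. State one expected number of bereaved surrogates and its follow-up window (9 months, or including the optional 12-month extension). Use it in sections 4.1, 8.1 and 9.2.
2. Recompute the six Aim 3 powers for that number. Name the method, the loss assumed before the 3-month survey, any baseline correlation used, and a cluster count that agrees with section 6.3.
3. Show the 80-death case beside it. With 19 clusters that is 0.57 to 0.61 (normal) or 0.52 to 0.56 (17 df), with a detectable difference of about 0.64 to 0.70 SD.
4. Reword the statement about post-death power to match the result.

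Optional and separate: name the surrogate's baseline HADS or PTSS-10 score, already collected, as a covariate in the Aim 3 model.

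The cost is text in three sections and one recomputed table block. No extra patients or data are needed, though the stated power may become less favourable.

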Recruitment will occur over 24 months beginning at the end of Year 1. We are highly experienced in recruiting seriously ill ESRD patients and their surrogates for research. Consent rates in our previous studies have been consistent at approximately 84% despite the studies' focus on end-of-life, the requirement that both patient and surrogate participate, and long-term follow-up. We expect a similar if not higher consent rate because the study involves a shorter follow-up time and minimal data collection directly from patients and surrogates. Based on our previous studies,¹⁸⁻²⁰ we conservatively anticipate that 427 patients (20%) will be *eligible and willing* to participate. To reach 400 dyads, we expect to enroll 21-22 dyads per cluster on average. These clinics each accept 10-70 new patients each year (total 700 additional patients), and thus our recruitment goal is readily achievable.

To Maximize Participant Retention, strategies found effective in retaining dyads over 12 months (dropouts, 3.8%) in our efficacy trial²⁰ will be used: we will

- a) obtain two backup contacts from each member of the dyad in the event that we cannot reach them by telephone and mail
- b) make confirmation phone calls 2 days prior to each follow-up
- c) make monthly check-in calls
- d) send holiday cards
- e) assign the same data collector whenever possible
- f) compensate each member of the dyad with gift cards (\$15 at baseline, \$15 at 2 weeks for the preparedness outcome assessment; \$20 at 3 months for the post-bereavement outcome assessment). Consistent with a pragmatic trial, participants will not be compensated for participating in the intervention. The Emory Study Coordination Center will be responsible for disbursement.

For Supplement Aims:

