6.3 MEASURES TO MINIMIZE BIAS: RANDOMIZATION AND BLINDING

Clinics covered by the same care provider who will deliver SPIRIT sessions will be combined to one cluster to avoid risk of contamination; this results in clusters (4 in GA, 3 in NC, 8 in NM, 5 in PA and 8 in VA). Because the numbers of available patients substantially vary across the clusters, to minimize group imbalance clusters will be stratified to three sizes: small (patient census ≤ 52), medium (53-105), and large (≥ 106). We will randomize clusters to either SPIRIT or usual care plus delayed SPIRIT, with randomly permuted blocks (sizes of 2 and 4) within cluster size stratum nested in each state, using a pseudo-random-number generator, by the Study Coordination Center.

Before the study starts, the Study Coordination Center will inform the group assignment for each cluster to the site PIs, with a unique ID consisting of abbreviations for state and cluster size stratum. While the heterogeneity in minority race/ethnicity across clusters improves the study's generalizability, stratification or pairing clusters by race/ethnicity is not feasible because some clinics uniquely serve one race with no comparable clinics within state. Group imbalances on race/ethnicity and other potential confounding factors will be examined and adjusted for in the analyses. The cluster randomized design prevents blinding patient-surrogate dyads and dialysis care providers to group allocation. However, research staff assessing effectiveness outcomes will be blind to group assignment.

For Supplement Aims:

[name] (biostatistician/Co-I) will generate a randomization scheme using stratified (by race), permuted block randomization with block size 5, using a random-number generator. Dyads will be randomized with equal allocation (1:1) to SPIRIT or usual care. Due to the nature of the intervention, blinding dyads to their group allocation is impossible, but the research staff assessing outcomes will be blind. Immediately after the completion of the baseline assessment by phone, the data collector will open a sealed envelope to identify group assignment and schedule an intervention session to take place ~ 2 weeks hence for SPIRIT as well as a follow-up data collection session in the next 2-3 days.

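### The power stated in 9.2 for the binary primary endpoints is not reproduced from the stated inputs: dyad congruence comes to about 0.81-0.85 and 0.71-0.77, against 0.92 and 0.84

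*Combined protocol and SAP*

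**What the plan says.** Section 9.2 describes the method: "We conducted a simulation study to estimate power with 2-sided significance level alpha=.05", "corrected for anticipated dropout and potential intraclass correlations (ICCs) ranging .01-.04". The model is "a generalized linear mixed model for binary outcomes (e.g., dyad congruence") and a linear mixed model for continuous ones. The table is headed "Power for comparing SPIRIT and usual care with 19 clusters". Its binary rows read:

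- Dyad congruence: 48%, OR 2.0, ICC 0.02 and 0.04, power 0.92 and 0.84.
- Composite: 47%, OR 2.0, ICC 0.02, power 0.93.

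The summary sentence is "The overall power to detect clinically meaningful differences is excellent for the primary outcomes and good for the post-death outcomes".

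Section 5.5 supplies the sample size: "To reach 400 dyads, we expect to enroll 21-22 dyads per cluster on average". That agrees with 19 clusters, since 400/19 = 21.05. Section 6.3 differs: "this results in clusters (4 in GA, 3 in NC, 8 in NM, 5 in PA and 8 in VA"), a sum of 28, with the total itself not given.

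Section 9.2 does not give the simulated number of dyads, the dropout rate, the scale of the ICC, the arm to which 48% belongs, or any baseline or covariate adjustment.

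**The concern.** With about 21 dyads per cluster, ICCs of 0.02 and 0.04 inflate the variance by about 40% and 80%. Power of 0.92 and 0.84 is hard to square with that for 400 dyads and an odds ratio of 2.0 from 48%.

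Dyad congruence is the first primary hypothesis in 9.1. Section 10.1.6 has the DSMB compare recruitment and sample characteristics with the power assumptions, and monitor the ICC to judge whether the trial will have its expected power. If the table is too favourable, the DSMB has the wrong benchmark. At ICC 0.04 it would assume a type II error of 16%, where the stated inputs give about 23-29%.

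**Working it through.** **Inputs.** Two-sided alpha 0.05, 19 clusters, 48% or 47%, OR 2.0 and the ICCs are from 9.2; 400 dyads is from 5.5. Equal arms are assumed, because 6.3 says "We will randomize clusters to either SPIRIT or usual care plus delayed SPIRIT, with randomly permuted blocks (sizes of 2 and 4"); a split of 9 against 10 clusters makes no material difference. The 48% is first read as the control rate.

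**Formulas.** Design effect DE = 1 + (400/K − 1) × ICC for K clusters. Effective n per arm = 200/DE. SE = √[(p1(1−p1) + p2(1−p2))/n]. Power = Φ(difference/SE − 1.96).

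**1. Dyad congruence.** OR 2.0 from 48% gives 0.96/(0.52 + 0.96) = 64.9%, a difference of 0.1686.

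| ICC | DE | n per arm | SE | Difference/SE | Power | Stated |
|---|---|---|---|---|---|---|
| 0.02 | 1.40 | 142.7 | 0.0578 | 2.92 | 0.83 | 0.92 |
| 0.04 | 1.80 | 111.0 | 0.0656 | 2.57 | 0.73 | 0.84 |

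A pooled-variance test gives 0.82 and 0.72.

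**2. Composite.** 47% and OR 2.0 give 63.9%. At ICC 0.02 power is 0.83, against 0.93 stated.

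**3. Do other rows of the table reproduce on 400 dyads in 19 clusters?** Here SE = √(2 × variance/n), with no adjustment. At ICC 0.10, DE = 3.01 and n = 66.5 per arm.

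- Decisional conflict: 0.24/√(2 × 0.23/66.5) = 2.89, power 0.82 (stated 0.81).
- Decision-making confidence: 0.22/√(2 × 0.20/66.5) = 2.84, power 0.81 (stated 0.80).
- At ICC 0.01 the same steps give 0.995 and 0.994 (stated 0.98 and 0.99). This is a looser check, because power is near its ceiling.
- The Aim 3 rows give 0.79-0.85 if about 145 bereaved surrogates are assumed (stated 0.78-0.85). That number is an assumption: 4.1 gives about 80 deaths and 8.1 about 160.

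**4. Other readings of the congruence row (400 dyads, 19 clusters unless stated).**

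| Reading | ICC 0.02 | ICC 0.04 |
|---|---|---|
| 48% as the SPIRIT rate, pooled test | 0.81 | 0.71 |
| ICC on the latent logit scale, formula | 0.84-0.85 | 0.75-0.76 |
| Simulated random-intercept logistic model, Wald z | 0.82-0.85 | 0.72-0.77 |
| Same simulation, t on 17 df | 0.78-0.82 | 0.68-0.73 |
| 427 dyads | 0.85 | 0.74 |
| 3.8% dropout (rate from 5.5), 385 dyads, formula | 0.80-0.84 | 0.70-0.75 |
| One-sided alpha | 0.88-0.89 | 0.80-0.82 |
| ICC read as a logit-scale variance | 0.90-0.91 | 0.87-0.88 |
| 28 clusters | 0.85-0.87 | 0.78-0.80 |

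No reading gives both 0.92 and 0.84. For 28 clusters, 400/28 = 14.29, so DE = 1.27 and 1.53.

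**5. What would reproduce the row.** If 25% of the variance is removed, n per arm rises to 142.7/0.75 = 190.3 and 111.0/0.75 = 148.0, and power becomes 0.92 and 0.84. The composite becomes 0.92. Across the readings of 48%, the reduction needed is about 25-28%.

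**The case against.** The strongest reply is that 9.2 reports a mixed-model simulation, not a design-effect formula, and that the simulation may have used information the table omits. The outcomes are measured at baseline and at 2 weeks, the 9.4.2 model includes covariates, and the prior-trial effects in 2.2 were adjusted for time and baseline values. Step 5 shows that one such assumption restores both congruence figures and brings the composite within 0.01. This stands as a possible explanation. But 9.2 states no adjustment, 9.4.2 does not list the baseline value of the outcome, and the continuous rows at ICC 0.10 reproduce without one.

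A reader might infer that clustering was left out, because 400 independent dyads give 0.93 for congruence. The documents do not support that. Stated powers of 0.92 and 0.84 imply standardised effects of 3.37 and 2.95, whose squared ratio is 1.30. The design-effect ratio at 19 clusters is 1.80/1.40 = 1.29. The fall between the two stated values is what clustering should produce, and an unclustered calculation could not give 0.84 at all. What differs is a roughly constant factor in the variance.

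A reader might also infer that the trial is underpowered and should enrol more. That goes too far. At ICC 0.02, z-based power stays at about 0.80 or above, and 9.2 says that effects were taken at 2 months because those at 2 weeks were larger.

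**Conclusion.** The point holds as a failure to reproduce. From the stated inputs, power for dyad congruence is overstated by about 0.07-0.11 at ICC 0.02 (0.81-0.85 against 0.92) and by about 0.07-0.13 at ICC 0.04 (0.71-0.77 against 0.84). For the composite the gap is about 0.10. The fall below 0.80 is at ICC 0.04. A t reference with few degrees of freedom lowers both figures further.

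These ranges assume 400 evaluable dyads, equal arms, z-based tests and no covariate adjustment. They cover the unstated ICC scale and either arm for the 48%. They do not show that the reported simulation was wrong, since it is not fully described. The 28-cluster figures are a sensitivity check: 28 is a sum of state counts, and the list in 6.3 includes NM, which the synopsis does not.

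**What to change.** 1. Reconcile the cluster count between 9.2 and 6.3, and the dyads per cluster in 5.5 with it.
2. Re-run the congruence and composite rows for that count, stating the number of dyads, dropout, ICC scale, reference arm and any adjustment. By the calculation above, congruence should be restated at about 0.83 and 0.73 if 19 clusters is right, or about 0.87 and 0.80 if 28.
3. If the simulation assumed a variance reduction from baseline or covariate adjustment (about 25% would be needed), say so with its basis, and put the baseline value of the outcome in the 9.4.2 model. Otherwise correct the figures.
4. Revise the description of power for the primary outcomes to match, and give the DSMB the corrected table for its power and ICC monitoring.

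An ICC 0.10 entry for the binary endpoints, as the continuous rows already have, is optional. The cost is one re-run of an existing simulation and a less favourable stated figure. Enrolment and endpoints do not change; the analysis changes only if item 3 adds the baseline value.

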Due to the exploratory nature of the study, a traditional sample size calculation was not performed. Instead, our goal was to provide estimates of effect sizes (standardized mean differences between pre- and during- COVID-19 study points) for the outcomes in aims 1-3. Preliminary power calculations based on a two-sample t-test, indicate that a sample size of 72 in the SPIRIT intervention and 35 in the usual care group achieve 80% power to detect a difference in mean changes of 0.5 between the groups. This calculation assumes a repeated measures design with a standard deviation of 1.0 at both time points, a between measurement correlation of 0.2 and a 5% significance level.

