Aim 1. Compare the stability of patients’ goals-of-care preferences over time, from pre-outbreak to during-outbreak, by group and estimate effect by race: We will use mixed effects modeling to assess differences in patients’ goals of care over time, from pre- to post-lockdown time points. We will sequentially build a longitudinal model that will include time, treatment group and race as fixed effects; then 2-way interactions of time x group, time x race, treatment x race, and finally a 3-way interaction of time x group x race, if the sample size permits. We will select the most parsimonious model using Akaike information criterion (AIC) and Bayesian information criterion (BIC). We will use contrasts to test whether participants demonstrated significant change in goals-of-care preferences across different combinations of treatment and race.

Aim 2. Assess the stability in the three preparedness outcomes, from pre-outbreak to during-outbreak by group, and estimate race effect: We will perform analyses similar to those described in Aim 1. In addition, for non-normal outcomes (binary, count) a generalized mixed effects model will be used. Appropriate contrasts will be used to assess differences in the outcomes over time by treatment groups, race and groups x race.

Aim 3. Examining the associations of the COVID-19 Related Stress, sex, race/ethnicity, and other sociodemographic characteristics to the level of changes in the preparedness outcomes and patient’s goals-of-care preference stability: We will use analysis of covariance to assess the relationship between COVID-19 related stress and changes in outcomes from T2 to T3 and T3 to T4, after controlling for the corresponding baseline values of the outcomes (i.e., T2 and T3 respectively). Using similar methods, we will evaluate whether there are disparate effects of sex, race/ethnicity and other sociodemographic factors on outcome changes and goals-of-care preference stability from T2 to T3 and T3 to T4, respectively

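### The COVID-19 cohort's stated 80% power for a 0.5 difference in mean changes does not follow from its own inputs, which give about 48% two-sided or 60% one-sided

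*Combined protocol and SAP*

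**What the plan says.** The supplement cohort part of section 9.2 says that no conventional sample size calculation was done because the study is exploratory, and gives its purpose: "Instead, our goal was to provide estimates of effect sizes". It then makes a specific power statement. The method is introduced as "Preliminary power calculations based on a two-sample t-test", and the result is that "a sample size of 72 in the SPIRIT intervention and 35 in the usual care group achieve 80% power". The quantity to be detected is a between-group difference in mean changes of 0.5. The assumptions are a repeated measures design with a "standard deviation of 1.0 at both time points, a between measurement correlation of 0.2 and a 5% significance level".

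Sidedness is not given for the cohort. Elsewhere in section 9.2 the parent trial's power is two-sided: "We conducted a simulation study to estimate power with 2-sided significance level alpha=.05". The cohort hypotheses for Aims 1 and 2 in section 9.1 are directional (smaller changes in the SPIRIT group).

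**The concern.** Every input except sidedness is stated, so the 80% can be checked directly. A low correlation between two measurements makes their difference more variable than either measurement alone. With a correlation of 0.2 the SD of a change exceeds 1.0, and 107 dyads split roughly 2:1 looked too few to give 80% power for a difference of 0.5.

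What is at stake is how the cohort's results are read. Someone relying on section 9.2 would take 0.5 as a difference that the cohort had a four-in-five chance of detecting, and could read a null result as evidence against a difference of that size. Under the plan's own inputs and a two-sided test, that chance is about one in two.

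**Working it through.** **Inputs (all from section 9.2, supplement cohort study):** group sizes 72 and 35; difference in mean changes 0.5; SD 1.0 at both time points; correlation 0.2; 5% level; two-sample t-test. Sidedness is not stated, so both cases are shown. No dropout inflation is applied, since none is stated.

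**Attempt to reproduce the stated 80%**

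1. SD of a change = sqrt(1² + 1² − 2 × 0.2 × 1 × 1) = sqrt(1.6) = 1.265.
2. Standard error of the difference in mean changes = 1.265 × sqrt(1/72 + 1/35) = 1.265 × 0.2061 = 0.2606.
3. Noncentrality = 0.5 / 0.2606 = 1.918, with 72 + 35 − 2 = 105 degrees of freedom.
4. Power from the noncentral t distribution: **0.476 two-sided, 0.603 one-sided**. The normal approximation gives 0.483 and 0.608. A simulation of 40,000 trials with bivariate normal data gives 0.478 and 0.603.

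The stated 80% is not reproduced. The shortfall is about 32 points two-sided or 20 points one-sided, too large to be rounding.

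**What would give 80% power**

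| Quantity solved for | Two-sided | One-sided | Plan |
|---|---|---|---|
| Detectable difference (72 and 35, correlation 0.2) | 0.737 | 0.652 | 0.5 |
| Correlation (72 and 35, difference 0.5) | 0.632 | 0.530 | 0.2 |
| Group sizes (difference 0.5, correlation 0.2, same ratio, normal approximation) | 155 and 75 | 122 and 59 | 72 and 35 |

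The detectable differences are 0.737 / 0.5 = 1.47 and 0.652 / 0.5 = 1.30 times the stated value, that is, 47% and 30% larger.

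**Expected precision.** The 95% confidence interval half-width is t(0.975, 105) × 0.2606 = 0.517, about as wide as the target difference.

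**Other readings tried (noncentral t)**

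| Reading | SD used | Two-sided | One-sided |
|---|---|---|---|
| Baseline-adjusted comparison (ANCOVA) | sqrt(1 − 0.2²) = 0.980 | 0.689 | 0.793 |
| Single visit, correlation ignored | 1.0 | 0.672 | 0.778 |
| Factor 2 omitted from the change variance | sqrt(1 − 0.2) = 0.894 | 0.767 | 0.853 |

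Each departs from the stated test, quantity or inputs, and none reaches 80% two-sided. The nearest match is a one-sided ANCOVA at 79%. The ANCOVA that the plan does describe is for cohort Aim 3 in section 9.4.2 ("We will use analysis of covariance to assess the relationship between COVID-19 related stress and changes in outcomes"), which is not the SPIRIT versus usual care comparison that section 9.2 powers. These readings may hint at where the figure came from, but the text does not support any of them.

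**The case against.** The arithmetic on the natural reading is not in dispute. The objections concern interpretation and weight.

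- **More than two measurements.** The cohort has two assessments before the outbreak (T1, T2) and two during it (T3, T4). If the two time points in section 9.2 meant two periods, each averaged over two visits with correlation 0.2 throughout, the change variance would be 0.6 + 0.6 − 2 × 0.2 = 0.8, and power 76.7% two-sided or 85.3% one-sided. This does not stand. Section 9.2 assigns SD 1.0 to each of two time points and mentions no averaging, the intervention falls between T1 and T2, and section 9.1 defines the Aim 1 changes as T2–T3 and T2–T4. The two-sided value would still be below 80%.
- **Small consequence.** The calculation is labelled preliminary, the cohort is exploratory and is listed in section 3 as not a clinical trial, and the pool of dyads is already fixed by the eligibility date. No stopping rule or parent-trial inference depends on it. This stands and limits the weight of the point. It does not make the stated figure correct.
- **The t-test is only a proxy.** Section 9.4.2 plans mixed models with time, group and race terms, and generalized mixed models for non-normal outcomes. This also stands: the replacement figures describe the calculation in section 9.2, not the exact power of the planned models.
- **Reporting precision is a preference.** An expected interval width is not needed to correct the arithmetic. That is fair, but it is the figure that matches the plan's own estimation goal.

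**Conclusion.** The concern holds. With the stated test, quantity, SD and correlation, 72 and 35 dyads give 47.6% power two-sided or 60.3% one-sided for a difference in mean changes of 0.5, against a stated 80%. The difference detectable with 80% power is 0.74 or 0.65.

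This rests on one measurement before and one during the outbreak, approximately normal changes, independent dyads and complete data. The two-sided figure is the natural comparator because it follows the parent trial's convention, but the conclusion is the same for a one-sided test. The effect is confined to an exploratory supplement; the parent trial's design and power are untouched. It should be corrected because a figure meant to guide interpretation does not follow from the inputs beside it.

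**What to change.** In the supplement cohort part of section 9.2:

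1. State whether the 5% test is one- or two-sided.
2. Restate the figure. If two-sided, 72 and 35 dyads give about 48% power for a 0.5 difference in mean changes, or 80% power for 0.74. If one-sided, about 60% power for 0.5, or 80% power for 0.65.
3. If a different correlation was intended (about 0.63 for a two-sided change-score test, 0.53 one-sided), or a different method such as ANCOVA, state it, justify it, and give the power it yields.
4. In keeping with the estimation goal, add the expected 95% confidence interval half-width of about 0.52, and say that the between-group difference will be reported with its confidence interval.

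The cost is one or two sentences and a less favourable stated figure. No extra dyads are needed and nothing in the parent trial changes.
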